9.1 Determination of sample size18

Abbreviations

AE	Adverse event
AESI	Adverse event of special interest
CRF	Case report form
DIR	Dose initially received
DMC	Data Monitoring Committee
eCRF	Electronic case report form
EU	European Union
FIX	Factor IX
FVIIa	Activated factor VII
FVIII	Factor VIII
FX	Factor X
FXa	Activated factor X
IgG2	Immunoglobulin G2
ISR	Injection site reaction
ITI	Immune tolerance induction
IV	Intravenous
LOS	Listing only set
mAb	Monoclonal antibody
MedDRA	Medical dictionary for regulatory activities
OD	On demand
PD	Pharmacodynamics
PK	Pharmacokinetics
PPS	Per protocol set
SAE	Serious adverse event
SAF	Safety (set)
SAP	Statistical analysis plan
SC	Subcutaneous
SD	Standard deviation
TF	Tissue factor
TFPI	Tissue factor pathway inhibitor
US	United States (of America)

1. Introduction

This SAP is based on Study Protocol version 2.0 (dated 26 JUN 2018).

Background

Hemophilia A and B are genetic bleeding disorders caused by the deficiency of Factor VIII (FVIII) or Factor IX (FIX), respectively. Persons with mild hemophilia (6% – 49% Factor level) may have excessive bleeding following dental procedures, injury or surgery, while moderate (1% to 5% factor activity) and severe (< 1% factor activity) hemophilia are typically characterized by more frequent and severe bleeding complications. Persons with severe hemophilia may experience not only bleeding after injury, trauma or surgery, but also spontaneous bleeding into joints, muscles and internal organs, including the brain. Recurrent bleeding into joints results in chronic debilitation.

The standard treatment for hemophilia A or B is replacement therapy, with intravenous (IV) administration of plasma-derived or recombinant FVIII or FIX, respectively. Some subjects treat bleeding episodes as they occur (i.e., on-demand [OD] treatment), while others treat themselves prophylactically to prevent bleeding according to the recommendations from the

World Health Organization. In recent years, prophylactic treatment has become the prevailing type of hemophilia treatment in most developed countries.

The proven clinical benefits of prophylaxis have led to a shift in treatment paradigm from OD treatment to the use of prophylaxis in many countries.

Better outcomes of prophylaxis versus OD treatment regimen are proven, but three major challenges characterize prophylactic treatment: the need for IV injections, the relatively high bleeding rate and the most significant treatment complication, the development of inhibitors.

Despite frequent and painful IV injections (and the subsequent frequent need for central venous access devices in young children), subjects on prophylaxis still bleed, with a median annualized bleeding rate of up to 6 bleeds, thus, leaving a high unmet medical need for better protection. A higher level of protection is in some cases achievable only by increasing the burden of treatment (more frequent injections), to reduce the clotting factor fluctuations that characterize replacement factors treatment (presence of peaks and troughs).

Effective treatment options are significantly lower if inhibitory antibodies against the FVIII or FIX (inhibitors) develop. The inhibitors interfere with the infused factor concentrates rendering them ineffective and requiring the use of more costly and less effective alternative hemostatic agents, defined as “bypassing agents”. The incidence of new FVIII inhibitors in subjects with severe FVIII deficiency is up to 45%. Inhibitor development is currently the most significant treatment complication seen in subjects with hemophilia. While improvements in hemostatic agents for subjects with inhibitors have resulted in decreased mortality, inhibitors are still associated with significant morbidity, including a higher rate of bleeding complications, increased disability, and a decreased quality of life.

As such, these bypassing agents are effective in most cases, but neither agent is universally effective and there is no prophylaxis option for subjects with hemophilia B and inhibitors, as NovoSeven is not licensed for prophylaxis in EU and US.

HEMLIBRA (emicizumab-kxwh) is currently approved in the US for subcutaneous routine prophylaxis in hemophilia A subjects with inhibitors, however, mimicking the action of activated FVIII (FVIIIa), it does not provide a steady state protection (variable rates of fluctuation with potential low levels at the end of the injection interval). Additionally, it carries a black box warning of thrombotic microangiopathy and thromboembolism when used with aPCC/FEIBA for the treatment of breakthrough bleeds.

There is currently no treatment available to provide constant protection against bleeding episodes, to lower burden of treatment, and to avoid risk of FVIII/FIX inhibitor development for the entire hemophilia population, regardless of the FVIII or FIX deficiency status or the presence of FVIII or FIX inhibitors.

BAY 1093884 may address all these unmet needs, representing a valid treatment option for all subjects with hemophilia.

The coagulation cascade and the role of tissue factor pathway inhibitor (TFPI)

In the cell-based model, the coagulation is initiated (the *Initiation Phase*) by the formation of a complex between the tissue factor (TF), exposed on the surface of fibroblasts as result of vessel injury, and activated factor VII (FVIIa), normally present in the circulating blood. The TF-FVIIa complex converts factor X (FX) in activated FX (FXa), which activates

prothrombin (FII) to thrombin (FIIa). In this *Amplification Phase*, due to this limited amount of thrombin, FVIII and FIX are activated and involved in the following *Propagation Phase*, where full thrombin generation takes place, enabling for clot formation.

According to this model, the TF *extrinsic pathway* is the principal cellular initiator of normal blood coagulation in vivo, and the major regulator of hemostasis and thrombogenesis, with the *intrinsic pathway* playing an amplification role.

In people with hemophilia, the TF initiated extrinsic coagulation pathway is intact, so a question may rise on why these people do bleed. The explanation is provided by the fact that the TF activity and the extrinsic pathway of blood coagulation are regulated by a specific and natural coagulation inhibitor: the tissue factor pathway inhibitor – TFPI.

In healthy individuals TFPI maintains a normal hemostatic balance (it is in fact considered a natural anticoagulant) while in people with hemophilia it further reduces the already insufficient thrombin due to the lack of FVIII or FIX.

Thus, the inhibition of TFPI through the administration of anti-TFPI antibodies (BAY 1093884) is expected to restore the hemostatic balance toward normal thrombin generation, and thus a potential mechanism to restore hemostasis in hemophilia subjects.

The product

BAY 1093884 is a human monoclonal IgG2 antibody with a novel mechanism of action based on blocking the function of endogenous TFPI.

TFPI usually consists of 3 Kunitz domains (K1, K2, K3). The primary anticoagulant properties of TFPI are mediated through the K1 and K2 domains. BAY 1093884 binds to both K1 and K2 domains, blocking TFPI inhibition of key factors (FXa via K2, and FVIIa/TF complex via K1) in the tissue factor initiated coagulation pathway. K3 binds to Protein S, which is not directly inhibiting the protease function.

BAY 1093884 has been optimized for affinity. The effect of neutralizing TFPI with BAY 1093884 has been evaluated and demonstrated in several in vitro and in vivo studies, showing prolonged efficacy compared to current bypass therapies. As a monoclonal antibody (mAb), BAY 1093884 also offers the opportunity of subcutaneous (SC) administration, while other currently available hemophilia treatments have to be administered intravenously.

The goal of TFPI inhibition is to restore normal levels of FXa, and thus correct the low levels of thrombin generated due to deficiency of either FVIII or FIX, independent of whether the deficiency results from ineffective production, or results from presence of inhibitory antibodies directed against either protein. TFPI inhibition targets a normal regulatory protein, and consequently is not a pro-coagulant. Thus, normal events that lead to initiation of coagulation at a site of injury are unaffected. Additionally, TFPI inhibition does not interfere with downstream mechanisms that protect from or turn off thrombin generation, thus regulation of thrombin and fibrinolysis remain intact, with a consequent favorable safety profile.

The overall nonclinical toxicology and safety profile of BAY 1093884 lends to support clinical studies with repeated administration of BAY 1093884 in subjects with hemophilia A or B with or without inhibitors.

Further details can be found in the Clinical study protocol, which contains comprehensive information on the study drug.

2. Study Objectives

Primary objective:

- To assess the safety and tolerability of multiple subcutaneous doses of BAY 1093884 in subjects with hemophilia A or B with or without inhibitors.

CCI

3. Study Design

This is an open-label Phase 2 study with multiple escalating doses of BAY 1093884 in 3 cohorts. The goal of the study is to evaluate the safety of multiple escalating doses of BAY 1093884 and identify a dose (or doses) to be used in the pivotal Phase 3 study.

The study has 2 main components - a multiple dose escalation component and a dose finding component.

Multiple-dose escalation component: Eight (8) new distinct subjects are planned to be enrolled in each of the 3 dose cohorts. Opening of the new cohort will only enroll new subjects. An initial dose of 100 mg SC has been selected for Dose X based on safety and PK/PD data from the Phase I study. Safety data from Dose X in N=6 subjects after 1x/week SC dose for 6 weeks will be the basis for opening the cohort for Dose Y. When acceptable safety and tolerability has been achieved in the first 6 subjects after 6 weeks of dosing, the cohort for Dose Y (not to exceed 250 mg) will be opened for enrollment of 8 new subjects. The opening of cohort to Dose Z (dose not to exceed 400 mg) follows the same process and will be based on safety/tolerability data from N=6 subjects given Dose Y once weekly for 6 weeks.

The DMC will review all available safety data and the proposed dose based on PK/PD prior to opening any cohort. Safety evaluation, including stopping criteria, is described in the Study Protocol.

Dose finding component: This portion of the study is designed to allow for identification of the appropriate dose(s) for the Phase 3 study. The dose selection for Phase 3 will be based on both the assessment of safety and evidence of efficacy based on bleeding control assessed over a 12 week period of dosing. In each cohort at dose level X, Y and Z the subjects will continue at that dose for at least 12 weeks and efficacy information from all 8 subjects at each dose level will be used for the assessment of efficacy (based on number of bleedings). Although acceptable safety and tolerability data of 6 weeks in at least 6 subjects at Dose X is required to open the next cohort – Dose Y, all 8 subjects at Dose X will remain at dose level X for at least 12 weeks to assess the efficacy. After 12 weeks of treatment with BAY 1093884, these patients (in dose level X or Y) will be allowed to escalate to the next dose level (if the next dose level is open), safety criteria as defined in the protocol are met, and the

patient experiences more than 2 bleeds during the first 12 weeks or more than 1 bleed at any 12 weeks interval after the first 12 weeks of dosing at a particular dose level. The safety criteria to be assessed for this portion of the study (individual dose escalation after 12 weeks of dosing in that particular dose cohort) are provided later in this section.

For each subject, the study is structured in three parts

Part A. Each subject will be treated with the allocated dose of BAY 1093884 (X mg, Y mg or Z mg) for 12 weeks. These first 12 weeks will allow for primary safety evaluations of each dose.

[figure not shown]
Part B. Each subject will be treated for additional periods of 12 weeks in duration. After evaluation of the number of bleeds at the end of each 12-week period, subjects can be treated with the same dose or with the next higher opened dose level. The date when the last subject in Cohort 3 (Z dose) has completed Part B, will be the database cut-off date (i.e., primary completion date).

Extension part. After completion of Part B of the Z dose cohort, and upon DMC evaluation of safety data from the first 6 patients for 6 weeks in the dose Z cohort, all subjects will be invited to continue the treatment in an extension part, at the end of their ongoing Part B period. During the extension, all subjects will be evaluated (number of bleeds) every 12 weeks and escalated to the next higher opened dose, if dose escalation criteria are fulfilled (as per Part B). The extension part will continue, pending submission of safety and efficacy data to Health Authorities after 12 months from its start and every 12 months thereafter, until Marketing Authorization.

Any bleeding event, which should occur during the study (including the extension part) and which requires additional control, will be treated with the subject’s pre-assigned treatment (by-passing agent or replacement factor) prescribed by the Investigator pre-study.

Figure 1 shows a schematic overview of the study design.

Figure 1 Design overview

DMC = Data Monitoring Committee.

- Black boxes: Part A: Initial 12 weeks of treatment with BAY 1093884 (no escalation)
- Grey boxes: Part B: all subsequent groups of 12 weeks of treatment with BAY 1093884 (first escalation allowed)
- White boxes: Extension part with evaluations every 12 weeks (further escalations allowed)

Statistical Analysis Plan

Protocol No.: **BAY 1093884 / 19580**

Page: 8 of 19

Solid line arrows:	Option for dose escalation, if the next higher dose is approved and the subject meets the escalation criterion (>2 bleeds in Part A).
Dotted line arrows:	Option for dose escalation, if the next higher dose is approved and the subject meets the escalation criterion (>1 bleed in 12 weeks).

At least 24 adult subjects (≥ 18 years of age) will be enrolled. If additional safety evaluation is needed, a maximum number of 40 subjects may be included.

Eight (8) new distinct subjects are planned to be enrolled in each of the 3 dose cohorts. Opening of the new cohort will only enroll new subjects. These subjects will be treated prophylactically with the X Y or Z dose of BAY 1093884 once weekly for 12 weeks (part A). At least 1 inhibitor subject (any titer) and 2 PK subjects (willing to undergo full PK evaluations) will be enrolled in each cohort.

All subjects of each cohort will continue on the dose assigned for Part A (12 weeks) to obtain safety data and also individual efficacy data.

Individual subject dose escalation criteria in the dose finding part of the study:

In this portion of the study, the objective is to identify the appropriate dose(s) for the Phase 3 study. The dose selection for Phase 3 will be based on both the assessment of safety and evidence of efficacy based on individual bleeding control assessed over a 12 week period of dosing for each patient.

Subjects will be evaluated for the number of bleeds occurring during each part of the study. In particular, only the bleeds recorded as “spontaneous” (not related to any trauma or activity) and requiring additional treatment will be considered for the dose escalation efficacy evaluation, and are defined below as “bleeds.”

Evaluation at the end of Part A:

Subjects who present ≤ 2 bleeds during Part A will start Part B and continue on the same weekly dose; otherwise (if presenting > 2 bleeds) subjects will escalate to the next higher opened dose cohort.

Evaluation at the end of every 12-week period of Part B and extension:

Subjects who present ≤ 1 bleed in 12 weeks, during Part B, or during the extension part, will continue on the same weekly dose; otherwise (if presenting > 1 bleed) subjects will escalate to the next higher opened dose cohort.

Since dose Z is the highest dose, any subject on dose Z who meets the escalation criteria described above may withdraw from the study or may continue treatment to provide further safety and efficacy data. The decision on treatment continuation is at the subject’s and investigator’s discretion.

The first injection of any new or escalated dose will be given under medical supervision.

If a subject qualifies for dose escalation based on the number of bleeds, but the next higher dose cohort has not been opened, the subject should stay on the current dose and then escalate to the next higher dose only after it is opened.

End of study

The end of the study as a whole will be reached as soon as the last visit of the last subject has been reached in all centers in all participating countries (EU and non-EU).

Primary completion

The primary completion event for this study is when the last subject in Cohort 3 has completed 24 weeks of treatment (end of Part B).

4. General Statistical Considerations

4.1 General Principles

The statistical evaluation will be performed by using the software package SAS release 9.2 or higher (SAS Institute Inc., Cary, NC, USA).

All data (efficacy, safety, PK/ PD, and demographic data) will be listed and study summary tables will be provided where appropriate. Variables measured on metrical scales will be summarized using descriptive statistics that will include: the number of non-missing observations, the arithmetic mean, the sample standard deviation, the median, the minimum and maximum, as well as the first and third quartiles where appropriate. Frequency tables will be provided for variables measured on ordinal or nominal scales. Tables will display the number and percentage of subjects falling within a particular category.

Data will be displayed by dose cohort and by study medication actually received during the respective study parts and their visits.

Data will be displayed by period of time. This includes:

- Part A: The first 12 weeks of treatment of each subject.
- Part B: The additional 12-week periods of treatment after Part A. Each subject will be analyzed in the dose cohort he was assigned to (data of dose escalated subjects will be not included).

In general, data will be displayed as measured at each scheduled time point, individual values will be presented in listings.

4.2 Handling of Dropouts

In this study, all efforts must be taken to engage patients to comply with all study procedures and to continue to be followed until the end of the study.

A subject who discontinues study participation prematurely for any reason is defined as a “dropout” if the subject has received at least 1 dose of BAY 1093884. A subject is regarded a “screening failure” if he terminates the study for any reason (e.g., failure to satisfy the selection criteria) prior to the time point used for the definition of “dropout” .

In all cases, the reason for withdrawal must be recorded in the electronic case report form (eCRF) and in the subject's medical records.

The number of subjects who prematurely discontinue the study during the treatment phase or during the post-treatment observation phase for any reason, as well as the reasons for premature discontinuation of study, will be displayed by dose cohort and dose actually received. Baseline characteristics will be displayed by premature discontinuation (yes/no) from study.

Subjects who drop from the study after first administration of study treatment will be included in a listing in addition to the inclusion into the SAF.

4.3 Handling of Missing Data

All missing or partial data will be presented in the subject data listing as they are recorded on the Case Report Form (CRF).

General rules

When appropriate, the following rules will be implemented so as not to exclude subjects from statistical analyses due to missing or incomplete data:

- **Efficacy Variables**

If the details of a bleed are missing (e.g., type of bleed spontaneous, non-spontaneous/non-traumatic or traumatic), the bleed will be counted for all categories of bleeds, but not for the corresponding subgroup of bleeds.

Each subject's bleeding period start date will be needed to allocate the bleedings to the respective period. If dates for bleeds and injections of rescue medication are both missing then these bleeds cannot be counted. If the bleed date is missing, but the injection date is available, injection date will be used.

- **AE Variables**

For the purpose of treatment-emergent flags, missing AE start day will be imputed as the 15th of the month. However, if the AE start day is missing, but the AE starts during the same month or on the same day as the first dose, but the AE start time is missing, the AE start day (and time in the second case) will be taken from first dose start day (and time). If both day and month of AE start date are missing, day and month will be imputed as the date of the first dose.

4.4 Interim Analyses and Data Monitoring

An independent Data Monitoring Committee will review safety data according to the DMC charter. No alpha adjustment is required. No interim efficacy analysis is planned.

After all subjects still participating in the study have completed Part A and at least one 12-week Part B period (primary completion) of the study, all dose levels will be assessed including clinical safety, routine safety laboratory, hemostasis and thrombosis markers as per PK/PD assessment and clinical efficacy.

4.5 Data Rules

All bleed and infusion data will be reported and imported into SAS. If an infusion is given for a bleed and the bleed information is not provided, the infusion date will be used as the bleed date. All bleeds include spontaneous bleeds and trauma. An untreated bleed is a bleed with no corresponding infusion for the bleed. Bleeds occurring before start of treatment with study medication will not be counted. Bleeds will be counted if at least one of the following information on bleed is available: parts of the date of bleed (as long as the information is sufficient that the bleed fits in the treatment period), given severity or response to treatment of bleed, type of bleed or information on treatment or reason for treatment.

4.5.1 Baseline values

Baseline values for vital sign measures and laboratory values are planned to be taken at Visit 2 before administration of study drug. If these values are not available, values taken before first administration of study drug will be considered (e.g., values taken on Visit 1). In case of

more than one available value before first administration of study drug, the non-missing value closest to Visit 2 will be taken.

4.5.2 Annualized bleed rate

Regarding the definition on the annualized bleed rate (see section 6.2.1) the following datetime will be used:

For annualized bleed rate for Part A, the first datetime of Part A will be the datetime of the first administration of study drug (Visit 2 – Start of BAY 1093884 treatment at the respective dose). The last datetime of Part A will be 1 minute before the datetime of the Visit 6 administration of study drug (the first administration of study drug in Part B). For subjects who discontinue the study during Part A, the last datetime of Part A is the datetime of the later of last visit and last administration of study drug.

For annualized bleed rate for each 12-week Part B period, the first datetime of the Part B period will be the datetime of the first administration of study drug in Part B (Visit 6) in case of first Part B period, or the datetime of the administration of study drug of Visit 7 or any subsequent 12-week visit. The last datetime of Part B will be 1 minute before the datetime of the administration of study drug of Visit 7 or the following subsequent 12-week visit. For subjects who discontinue the study during Part B, the last datetime of Part B is the datetime of the later of last visit and last administration of study drug.

For annualized bleed rate for period on dose initially received (DIR), the first datetime on DIR will be the datetime of the first administration of study drug (Visit 2 – Start of BAY 1093884 treatment at the respective dose). The last datetime on DIR will be 1 minute before the datetime of the administration of the next higher dose of study drug (Visit 6 or Visit 7). For subjects who discontinue prior to administration of the next higher dose or never met the dose-escalation criteria, the last datetime on DIR is the datetime of the later of last visit and last administration of study drug.

4.5.3 24 hours rule

Count no more than 1 bleed in a calendar day. If there is more than 1 bleed in a calendar day, to determine the bleed that gets counted, give priority to treated bleeds, spontaneous or trauma bleeds, then joint bleeds. Otherwise, count the first bleed in the day. Severity and treatment response will come from this selected bleed. Bleed site will be aggregated over all bleeds from that day. Regardless of which bleed is selected, the time of the first bleed in the day will be used. All other infusions in the day for treating bleeds will be considered follow-up infusions.

If more than one prophylaxis injection is given on a calendar day, the data of all prophylaxis injection will be combined to one injection and the time will be taken from the first prophylaxis injection of that day.

4.5.4 72 hours rule

Do not count a spontaneous joint/muscle bleed if it occurs within 72 hours of a bleed (or infusion for that bleed) at the same site. For a bleed to be affected by this rule, all sites listed on the bleed must also be specified in the previous bleed. If the current and previous bleeds are both skin/mucosa bleeds, this rule does not apply. Such infusions for bleeds will be considered to be follow-up infusions.

Joint bleeds can occur in more than 1 joint site. For each joint bleed, count all sites (combining left and right). For the table showing the Joint Site frequency, sum counts over all sites.

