05 APR 2019

Version 4.0

Page: 9 of 96

Frequency tables will be provided for variables measured on ordinal or nominal scales. Tables will display the number and percentage of subjects falling within a particular category.

Data will be displayed by dose level and by study medication actually received during the study parts and the corresponding visits.

Safety

Vital signs, AEs and laboratory data will be analyzed by descriptive statistics. All AEs will be tabulated according to the affected system organ class and preferred term, as coded by Medical Dictionary for Regulatory Activities (MedDRA). Separate descriptions will be delivered for the different dose levels. Special interest will be given to safety observations after application of rescue medication during the treatment phase with BAY 1093884.

Efficacy

CCI

The main focus will be the number of spontaneous bleeds requiring additional treatment.

Further details of Efficacy analysis are listed in the Statistical Analysis Plan (SAP).

Protocol amendment summary of changes

Table of main changes

Section # and name	Description of change	Brief rationale
Section 2 Synopsis Section 6.1 Inclusion criteria	Inclusion criterion 1 was modified to further specify that only subjects diagnosed with severe hemophilia, with or without inhibitors, are eligible.	Criterion updated to ensure that only hemophilic patients who are diagnosed as severe are included in the study.

Typographical, grammatical, and other minor edits are not identified.

Table of contents

Cover page of the integrated protocol.....	1
1. Title page	2
Signature of the sponsor’s medically responsible person.....	3
Signature of principal investigator.....	4
2. Synopsis.....	5
Protocol amendment summary of changes.....	10
Table of tables	14
Table of figures.....	14
List of abbreviations	15
3. Introduction.....	17
4. Study objectives.....	20
5. Study design.....	21
6. Study population	26
6.1 Inclusion criteria	26
6.2 Exclusion criteria.....	26
6.3 Withdrawal of subjects from study.....	27
6.3.1 Withdrawal.....	27
6.3.2 Replacement	28
6.4 Subject identification.....	28
7. Treatments.....	29
7.1 Treatments to be administered.....	29
7.1.1 Prophylaxis treatment with BAY 1093884	29
7.1.2 Treatment of bleeds.....	30
7.1.3 Treatment for PK/PD assessments.....	31
7.1.4 Treatment for minor and major surgery	31
7.2 Identity of study treatment.....	32
7.3 Treatment assignment.....	33
7.4 Dosage and administration	33
7.4.1 Selection of doses in the study	33

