7.1.2 Treatment of bleeds

The occurrence of bleeds of different cause, severity and site is a typical characteristic of subjects with hemophilia, being the clinical manifestation of the disease itself.

Bleeds will be classified into the following types:

- **Spontaneous:** Not attributable to any trauma or activity
- **Non-spontaneous/non-traumatic:** Not related to a trauma, but due to activity (walk, run, sport, gym, etc.)
- **Traumatic:** Related to an identified trauma

Throughout the study, all bleeds will be recorded, but only the bleeds recorded as “spontaneous” (not related to any trauma or activity) and “requiring additional treatment” will constitute the base for the efficacy evaluation.

All bleeds occurring in subjects receiving prophylactic treatment with BAY 1093884 after Visit 2 (“Start of treatment with BAY 1093884”) which require additional treatment will be treated according to the subject’s pre-study treatment as outlined in Section 8.1. Given the potential additive effect of BAY 1093884 and concomitant medication, it is recommended to treat the bleeds with the lowest approved doses of the prescribed replacement factor or bypassing agent, and repeat the dose, if additional doses will be needed, at the investigator’s judgment.

For the same reason, the investigator must carefully consider the intensity and the location of a trauma for which bleeding has not yet occurred before the preventive use of a replacement factor or a bypassing agent during treatment with BAY 1093884. Careful oversight of bleed treatment by the Investigators will ensure the patients’ safety.

If a bleed occurs on a day of the planned injection of BAY 1093884, the subject should treat the bleed with his usual medication and administer the scheduled prophylactic injection of BAY 1093884. The injection schedule with BAY 1093884 will not be affected by the treatment of bleeds.

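### The 24-hour rule puts spontaneous and traumatic bleeds in one tier, so a treated traumatic bleed can displace a same-day treated spontaneous bleed from the key efficacy count (minor)

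*SAP*

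**What the plan says.** SAP 4.5.3 sets a daily cap: "Count no more than 1 bleed in a calendar day". When several bleeds fall on one day, the instruction is to "give priority to treated bleeds, spontaneous or trauma bleeds, then joint bleeds". If that does not settle it: "Otherwise, count the first bleed in the day".

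Little survives from the bleeds that are not selected. Severity and treatment response come from the selected bleed. Site is pooled: "Bleed site will be aggregated over all bleeds from that day". Bleed type is not carried over, and the treatment of a displaced bleed is absorbed: "All other infusions in the day for treating bleeds will be considered follow-up infusions".

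Protocol 7.1.2 defines three types: spontaneous, non-spontaneous/non-traumatic, and traumatic. It says that only spontaneous bleeds needing additional treatment "will constitute the base for the efficacy evaluation". The efficacy paragraph of the protocol synopsis agrees: "The main focus will be the number of spontaneous bleeds requiring additional treatment". The three responder variables in SAP 6.2 (at most 2 in Part A, at most 1 in each 12-week Part B period, and none) all count treated spontaneous bleeds.

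The additional SAP of March 2020 (section 1) applies the same 24-hour rule to its bleed counts and annualized rates, and shows spontaneous bleeds separately.

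**The concern.** The sort order does not protect the bleed type on which efficacy is judged. Treated spontaneous and treated traumatic bleeds are equal at the first two criteria, so joint location and then clock time decide which is kept. Neither has any bearing on whether a treated spontaneous bleed occurred that day. No readable part of either document says that the rule works within bleed type, or that the data are restricted to spontaneous bleeds first.

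At stake are the spontaneous bleed counts, the spontaneous annualized rate and the responder proportions. One lost bleed can move a subject across a cut-off: 3 to 2 in Part A, 2 to 1 in a Part B period, or 1 to 0 for the bleed-free variable. The escalation criteria in protocol section 5 use the same cut-offs without mentioning a 24-hour rule, so a subject's analysed status could also differ from the count used at the site. The two counts should be reconciled.

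**Working it through.** The plan states no figure for this rule, so there is none to reproduce.

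**Inputs from the documents.** The cap, order and tie-break come from SAP 4.5.3, the three bleed types from protocol 7.1.2, the responder cut-offs from SAP 6.2, and the cohort size of 8 from SAP section 3. Part A and each Part B period last 12 weeks = 84 days.

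**Assumptions, not in the documents.** Bleeds are independent and Poisson, and all are treated. The joint share is the same for both types (70% in the simulation). Each subject has s spontaneous and t traumatic bleeds in 84 days, with (s, t) = (1, 1), (3, 2) or (4, 3).

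**Step 1: which pairings lose the spontaneous bleed.** The rule as a sort key is: treated, then spontaneous-or-traumatic, then joint, then earliest. Pair one treated spontaneous bleed with one same-day traumatic bleed and vary spontaneous joint yes/no, trauma treated yes/no, trauma joint yes/no and which came first: 2 × 2 × 2 × 2 = 16 cases. With a treated traumatic bleed, the spontaneous bleed is:

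| Spontaneous | Traumatic (treated) | Spontaneous first | Trauma first |
|---|---|---|---|
| joint | joint | kept | lost |
| joint | not joint | kept | kept |
| not joint | joint | lost | lost |
| not joint | not joint | kept | lost |

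That is 4 of 8. With an untreated traumatic bleed it is 0 of 8, so 4 of 16 overall. Against a non-spontaneous/non-traumatic bleed it is 0 of 16, because that type ranks below the shared tier. These are logical cases, not probabilities.

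**Step 2: expected loss.** With joint share p in both types, the chance that a treated pair loses the spontaneous bleed is ½p² + ½(1−p)² + p(1−p) = ½, whatever p is. Expected loss per 8 subjects ≈ 8 · s · t / 84 · ½:

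- (1, 1): 8 · 1 / 168 = 0.05 (simulated 0.04)
- (3, 2): 8 · 6 / 168 = 0.29 (simulated 0.27)
- (4, 3): 8 · 12 / 168 = 0.57 (simulated 0.55)

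The simulation used 60,000 subjects per scenario. As a share of spontaneous bleeds the loss is about t/168: 0.6%, 1.2% and 1.8%. From the simulated losses, the mean annualized rate is understated by 0.04/8 × 365.25/84 = 0.02 to 0.55/8 × 365.25/84 = 0.30 bleeds per year.

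**Step 3: responder status.** At the Part A cut-off a subject flips when exactly 3 spontaneous bleeds occur and one is lost, about P(S = 3) · 3 · t/168:

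- (1, 1): 0.0613 · 3 · 1/168 = 0.1%
- (3, 2): 0.2240 · 3 · 2/168 = 0.8%
- (4, 3): 0.1954 · 3 · 3/168 = 1.0%

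The simulated range is 0.1% to 1.1% of subjects, or about 0.01 to 0.09 subjects per cohort of 8.

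**Step 4: what one flip would do if it occurred.** With all 8 analysed, one flip is 1/8 = 12.5 points, for example 4/8 = 50% (90% Clopper-Pearson 19.3% to 80.7%) to 5/8 = 62.5% (28.9% to 88.9%). For one subject, one bleed in 84 days is 365.25/84 = 4.35 per year.

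**Step 5: after the change.** With spontaneous ranked above traumatic among treated bleeds, 0 of the 16 pairings lose the spontaneous bleed.

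**The case against.** The best defence is size. The expected shift in a responder proportion is about 0.1 to 1.1 points, against a planned interval about 60 points wide at n = 8. The 12.5-point step is the granularity of a cohort of 8, not the expected effect. The rates are assumed, and taking every traumatic bleed as treated makes the figures high for the independence model; clustering of bleeds would work the other way. Safety is primary, no hypothesis is tested, and individual listings keep displaced bleeds visible. All of this stands and sets the grade at minor.

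Parts of the efficacy text are redacted, and the additional SAP points to program code from other products, so programs may filter to spontaneous bleeds first. That limits what can be said about results; it does not correct the written rule. One could also say that spontaneous is named first and so ranks first, but the text joins the two types with an or and opens the next tier with then. If that is ambiguous, it still needs settling.

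A reader might infer more than the documents support:

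- *Any same-day traumatic bleed removes a spontaneous one.* It must itself be treated and meet the joint or timing condition.
- *Non-spontaneous/non-traumatic bleeds have no place in the order.* They rank below the other two types.
- *The rules can only ever lower the spontaneous count.* This holds for the selection step alone. Suppose a knee bleed is followed next day by a treated spontaneous knee bleed and an untreated elbow trauma. If the 24-hour rule runs first, the selected bleed carries both sites. It then escapes the 72-hour rule in SAP 4.5.4, which requires all its sites to be in the previous bleed. Without pooling of sites it would have been suppressed. The SAP does not fix the order of the two rules.
- *The results are biased towards the drug.* There is no control group. Proportional losses grow with the bleed rates in the scenarios above, so they could shrink differences between doses. If the rule also acted on the six-month pre-study period, it could shrink a before/after contrast. Only the absolute on-treatment figures are exposed in the favourable direction.

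**Conclusion.** The point holds, as a minor one. Followed as written, SAP 4.5.3 can give a wrong value for the count that the protocol makes the basis of efficacy: a day with a treated spontaneous bleed can be recorded as a traumatic-bleed day. The selection step can then understate the absolute on-treatment spontaneous count and annualized rate, and overstate the responder proportions.

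The logic rests on the SAP wording alone. The size rests on the assumed rates, independence and all bleeds treated: about 0.04 to 0.55 bleeds per cohort of 8 in 12 weeks, and about 0.1% to 1.1% of subjects reclassified. The actual same-day frequency is unknown. Nothing here shows that a conclusion about the drug or the choice of dose would change.

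**What to change.** In SAP 4.5.3, state that among treated bleeds on one calendar day a spontaneous bleed is selected before any other type, and only then apply the joint and first-in-day criteria. Keep the one-bleed-per-day cap for the all-bleeds count, and use the same order in the additional SAP. Running the rule separately within each type would also protect the spontaneous count, but it would break the cap for all bleeds, so the re-ranking is cleaner.

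The cost is one sentence and one sort key; SAP 4.6 already provides for an amendment or supplement. The all-bleeds count does not change. Counts of traumatic bleeds may fall slightly, because on shared days the traumatic bleed is now the one not counted. It would help to report on how many subject-days the selected bleed changes, which replaces the assumed frequency with an observed one.
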